- 5. Associated syndrome, including Marfan Disease or Neurofibromatosis
- 6. Sanders bone age greater than 4
- 7. Thoracic curve less than 35 degrees
- 8. Lumbar curve greater than or equal to 35 degrees
- 9. Unable or unwilling to firmly commit to returning for required follow-up visits
- 10. Investigator judgement that the subject/family may not be a candidate for the intervention

Number Of Subjects

Study Duration

Study Phases:

Screening

Study Treatment

Post-op Follow-Up

The study will be conducted at The Nemours – Alfred I duPont hospital for Children, Division of Orthopedics. Subject inclusion will be based on interest of patients that satisfy the inclusion/exclusion criteria that present to the Orthopedic Clinic. The total study enrollment will be 30 subjects. In the retrospective arm we will aim to enroll all patients who had the tether surgery in the past. The study ends when all patients reach skeletal maturity. Each subject's active participation will last about 5 years after surgery. The entire study is expected to last at least 8 years.

- 1. Screening phase: Subjects will be screened by study staff during a clinical visit in the Orthopedics department. Eligible subjects will be approached and if interested, enrolled during a routine clinical exam.
- 2. Study Treatment: The subject will undergo surgical intervention using accepted standard-of-care anterior approach using the Globus Medical Inc. CreoTM Stabilization System. Vertebral body tethering using screws and Polyethylene Terepthalate cord (Globus Medical, Inc. Reflect/TransitionTM Stabilization System) is investigational.
- 3. Post-operative Follow-up: Subjects will be followed at regular time points at 45 and 90 days post-op during the post-operative phase. Patients will also be seen at visits 180, 365, 730, 1095, 1460, 1825 days post-op during the extended follow-up phase.

Efficacy Evaluations

The primary efficacy evaluation measurement is thoracic Cobb angle (to nearest degree) at the pre-operative visit to Cobb angle during follow-up, especially at two years post-op (POD 730).

Safety Evaluations

We will use phase-specific endpoints to measure safety: 1) Study treatment phase: Any individual-level intraoperative events including neuromonitoring events (loss or change in neurological signaling or function), unanticipated events during surgery, and SAEs.

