After all of the screws are placed, the caudal 15mm port is used to pass the PET cord (Reflect/*Transition* TM *Stabilization System*, Globus Spine, Inc.) through the tulips of all of the screws. The set screw (*Creo* TM *Stabilization System*, Globus Spine, Inc.) is then placed on the most caudal screw tulip using a T-handle pusher. The set screw is locked in place using a locking cap (*Creo* TM *Stabilization System*, Globus Spine, Inc.), thereby securing the PET cord on the most caudal screw. Correction is achieved by tensioning the PET cord and through translation of the spine. Once the correction achieved is satisfactory to the surgeon, the set screws are tightened on each screw tulip- moving caudad to cephalad. Flouroscopic images should be obtained after each screw is tightened, to confirm curve correction. These fluoroscopic images also confirm that there is no pulling out, plowing, or other untoward changes in the screw placements in the vertebral bodies.

Once all screws have been tightened, global AP and Lateral X-rays of the spine should be performed to confirm correction of the curvature. Once satisfactory correction is

confirmed in this manner, the PET cord should be trimmed, to leave about 2cm at either end to accommodate any future adjustment if necessary. An attempt should be made to re-approximate the pleura, though this is difficult with the implant. A chest tube should be placed in one of the 5mm port sites. The hemithorax is then irrigated, the lung is re-inflated under direct vision, and the incisions are closed in layers.

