3.4 Study Population

3.4.1 Inclusion Criteria

- 1) Males or females age 8 to 16 years old at time of enrollment (inclusive)
- 2) Diagnosis of Idiopathic Scoliosis
- 3) Sanders bone age of less than or equal to 4
- 4) Thoracic curve of greater than or equal to 35 degrees, but no bigger than 60 degrees
- 5) Lumbar curve less than 35 degrees
- 6) Spina bifida occulta is permitted
- 7) Spondylolysis or Spondylolisthesis is permitted, as long as it is non-operative, the patient has not had any previous surgery for this, and no surgery is planned in the future
- 8) Completed standard-of-care procedures as outlined in Section 5
- 9) Subject consent and (if applicable) assent

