5.3 Efficacy Evaluation

The mode of efficacy evaluation for this procedure will be measurement of Cobb Angle. Cobb Angle is a coronal plane radiographic measurement of curvature of the spine. This angle will be recorded for the pre-operative coronal spine radiograph, as well as all subsequent serial radiographs. The change in Cobb angle (reduction) will be the primary evaluator of efficacy. 'Overall study success' of the intervention will be defined by a final Cobb angle of less than or equal to 50 degrees by the time subject reaches skeletal maturity.

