6.3.3 Efficacy Analysis

The primary analysis will be based on an intention to treat approach and will include all subjects who have undergone the intervention.

The endpoint used for efficacy will be change in post-operative Cobb angle compared to preoperative Cobb angle, measured on coronal radiograph of the spine. Considering change in Cobb angle is a continuous variable, repeated measures Anova or t-test will be used to detect any change in Cobb angle post-operatively. Linear regression will be utilized to assess which variables are associated with change in post-operative Cobb angle.

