6.6.2 Stopping rules for SAEs that are device-related
Definition of Terms:
□ Screw failure – screw and/or centering staple have loosened from the vertebra AND require re- operation
☐ Tether failure – the tether has broken or lost tension. Diagnosed at any time point after 3 months by increased angulation at a disc space on standing PA or increase in disc wedging on side bending x-ray to the side away from the implant. Also, it is only an SAE if noted before maturity AND overall Cobb worsens compared to the first erect measurement
☐ Implant re-operation - any problem with the implant that requires re-operation including re-operation for overcorrection with any of the following: a removal of all or part of the implant, loosening of the tension on the implant, or spinal fusion.

Stopping Points
☐ Screw failure stopping point: 3 of first 5 cases, 5 of first 10, or 25% of patients beyond 20
cases
☐ Tether failure stopping point: 3 of first 5 cases, 5 of first 10, or 25% of patients beyond 20
cases
☐ Implant failure re-operation stopping point: occurs in 4 of first 5 cases or greater than 50% of
cases beyond 10 cases

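### Efficacy is tested only as change from the pre-operative Cobb angle, with no visit or contrast named, so the test alone cannot show that the surgical correction is held during growth

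*Combined protocol and SAP*

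**What the plan says.** Section 6.3.3 (Efficacy Analysis) states: "The endpoint used for efficacy will be change in post-operative Cobb angle compared to preoperative Cobb angle". On method it adds that "repeated measures Anova or t-test will be used to detect any change in Cobb angle post-operatively". Sections 6.2 and 6.3.3 name no visit, direction or minimum size of change, and section 6.4 states that there is no effect size or power analysis. Emphasis on two years (POD 730) appears only in the Protocol Synopsis, under Efficacy Evaluations.

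Section 1.2.3 (Surgical Technique) describes where the first reduction comes from: "Correction is achieved by tensioning the PET cord and through translation of the spine". The end point of tensioning is the surgeon's judgement: "Once the correction achieved is satisfactory to the surgeon, the set screws are tightened on each screw tulip".

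Three other places bear on what happens later:

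- Section 5.3 defines overall study success as a "final Cobb angle of less than or equal to 50 degrees by the time subject reaches skeletal maturity", and has the angle recorded on the pre-operative and all later radiographs.
- The synopsis (Safety Evaluations) lists over-correction, implant failure, progression beyond 50 degrees at five years, and re-operation.
- Section 6.6.2 counts tether failure as an SAE only if, among other conditions, "overall Cobb worsens compared to the first erect measurement".

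The last of these is the only use of an early post-operative film as a reference. Section 6.3.3 does not use it.

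**The concern.** The operation produces a reduction before follow-up begins. A null hypothesis of no change from the pre-operative film is therefore largely answered in the operating room. Sections 1.1.1 and 1.4.1 argue for something that takes longer: that the tether modulates growth and keeps immature curves from passing 50 degrees. A single comparison with the pre-operative film adds the surgical correction to whatever follows, so a large correction that is then partly lost and a smaller one that is fully held can give the same result.

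The two permitted analyses also answer different questions. An ANOVA over all visits is an omnibus test. It is driven by the difference between the pre-operative film and all later ones, and a later rise in the angle adds to the variation between visits. It says that the visit means differ, not that correction persists. A t-test answers a question about one visit, but the plan does not say which. At stake is whether a reader of the efficacy result could see loss of correction in it.

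**Working it through.** The plan states no power, alpha or SD for efficacy, so there is no figure of its own to reproduce.

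**Inputs from the documents.** n = 30 over both arms (section 3.3.2, which also says there is no target enrolment). Mean treated curve of 44 degrees in the cited tethering series (section 1.4.1). 56% mean correction in the cited five-year thoracoscopic fusion results (section 1.3.1), used only as the upper end of a range.

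**Assumptions.** Two-sided alpha 0.05; complete follow-up; SD of change 5 to 12 degrees; initial correction 30% to 56%.

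**Step 1: smallest significant mean change.** For a paired t-test this is t(0.975, n−1) × SD / √n, with t(0.975, 29) = 2.045 and √30 = 5.477.

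- SD 5: 2.045 × 5 / 5.477 = 1.9 degrees
- SD 10: 2.045 × 10 / 5.477 = 3.7 degrees
- SD 12: 2.045 × 12 / 5.477 = 4.5 degrees

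**Step 2: how much correction can be lost with significance kept.** Largest loss = initial correction − threshold from step 1, starting from a mean of 44 degrees.

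| Initial correction | First standing mean | Loss at SD 5 | Loss at SD 10 | Loss at SD 12 |
|---|---|---|---|---|
| 30% (13.2) | 30.8 | 11.3 (86%) | 9.5 (72%) | 8.7 (66%) |
| 50% (22.0) | 22.0 | 20.1 (92%) | 18.3 (83%) | 17.5 (80%) |
| 56% (24.6) | 19.4 | 22.8 (92%) | 20.9 (85%) | 20.2 (82%) |

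At a wider SD of 15 the threshold is 5.6 degrees, and the share that can be lost is 58%, 75% and 77% in the three rows. With 15 patients the threshold is 4.4 to 8.3 degrees for SDs of 8 to 15.

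**Step 3: one invented path.** Means of 45 pre-op, 25 on the first standing film and 38 at POD 730. Surgical change −20, later change +13, net −7. At SD 10 the planned test gives t = 7 / (10 / 5.477) = 3.83, p = 0.0006. At SD 12, t = 3.20. Both exceed 2.045.

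**Step 4: simulation of the two permitted analyses.** 30 patients, nine films from pre-op to POD 1825, 1,500 runs per scenario. Assumed between-patient SD 6, residual SD 5, SD of patient-specific drift 0 to 12 degrees. The ANOVA used the most conservative (lower-bound) sphericity correction.

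- 44 → 22 → 33 at POD 730 (half lost): the test against pre-op shows significant improvement in about 100% of runs. A test against the first post-operative film shows significant worsening in about 100% of the same scenario's runs.
- 44 → 30.8 → 37.4 (30% correction, half lost): 93–100% and 96–100%.
- All correction lost by POD 1825: the ANOVA is significant in 100% of runs and the POD 730 t-test in 99–100%. A POD 1825 t-test shows improvement in only about 2%.

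**Step 5: does the success definition close the gap?** Entry is: "Thoracic curve of greater than or equal to 35 degrees, but no bigger than 60 degrees". A patient entering at 35 can gain 50 − 35 = 15 degrees and still be a success. If baselines were spread evenly (an assumption), (50 − 35) / (60 − 35) = 60% would start at or below 50 degrees.

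**The case against.** The pre-operative reference fits the stated objective. Section 2.2 asks about post-operative correction of the curve, and change from pre-op measures that. Growth modulation is rationale, not an objective.

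Late net change is also informative in itself. In the 45/25/38 example, Table 3 projects that a 45-degree curve passes 50 degrees in 100% of cases at Sanders stages 1 to 3 and in 88% at stage 4 (interval 2% to 100%). Against that, 38 degrees at two years may be a benefit. This stands, and it is why the comparison with pre-op should stay.

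A reader might infer that the trial would declare efficacy on a significant t-test while curves worsen. The documents do not say so. Section 5.3 ties success to the final angle at maturity, section 6.4 calls the work exploratory, and nothing makes the p-value the basis of a claim. A reader might also infer that the test can never fail. Step 4 shows that a t-test at a late visit does fail when all correction is lost.

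Later loss is partly captured as safety: progression beyond 50 degrees, re-operation, and tether failure with worsening, with exact intervals for device-related events in section 6.3.2. These count events. They do not estimate how many degrees of correction are kept, and section 6 gives the success proportion no estimate or interval.

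Finally, resting efficacy on change since the first standing film would be a poor replacement. A tether that corrects and holds perfectly scores zero, and drift into over-correction looks like gain. That argues for adding the contrast beside the others, as proposed below.

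**Conclusion.** The gap is real but limited. Section 6.3.3 names neither visit nor contrast, and its only reference is the pre-operative film. An early or all-visit test is almost sure to be significant. A POD 730 test needs a net mean change of only 1.9 to 4.5 degrees at n = 30 and SD 5 to 12, which from a 44-degree mean leaves room to lose roughly 66% to 92% of the correction over the range assumed. By itself the test cannot show that correction is held.

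The stronger reading, that change from pre-op is the wrong endpoint or carries no information, is not supported: it matches section 2.2 and gains meaning at late visits. Naming the visit helps but does not close the gap, because most of the correction can go before a POD 730 test fails.

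The degree figures rest on an assumed SD, alpha and initial correction and on 30 complete patients. The direction of the conclusion holds over the ranges shown.

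**What to change.** In section 6.3.3:

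1. Name POD 730 as the main efficacy visit, as the synopsis already stresses, and the final film as a further one.
2. From one repeated-measures model, report with 95% confidence intervals: (a) pre-op to first post-operative standing film; (b) that film to POD 730 and to the final film; (c) net change from pre-op at the same two visits. Since (a) + (b) = (c), the reader sees how much correction was obtained and how much was kept.
3. Report the proportion with Cobb angle at or below 50 degrees at skeletal maturity, with an exact 95% confidence interval.
4. Define the first standing film, using the POD 45 film where no earlier one exists. The intraoperative images in section 1.2.3 are not standing films and should not serve.
5. Present over-correction separately, so that it does not count as gain in (b).
6. State that the efficacy conclusion will not be drawn from the pre-operative test alone.

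No new visit or radiograph should be needed, because section 5.3 already records the angle on all serial films. The cost is SAP wording, a definition of the reference film that also works for retrospective patients, slightly more analysis, and an efficacy statement that may be less favourable.

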6.4 Sample Size and Power

The purpose of this study is to longitudinally follow a cohort of patients treated with a novel use of an implant, to explore safety and efficacy of the implant. The regulatory status of such an implant requires that we obtain an IDE. There is no comparative group and thus no effect size or power analysis associated with the work.

6.5 Interim Analysis

The study team will perform interim analyses based on the stopping rules listed in section 6.6 (below). If any of these rules are met, the study will halt enrollment until appropriate measures can be put in place to reduce patient risk. All reporting of AE/SAEs during the study will adhere to the guidelines in Section 8 (Safety Management).

6.6 Stopping Rules

☐ SAE in all of the first 5 patients or

The stopping rules for this study will be based on the prevalence of SAEs. There is special consideration given to SAEs that are found to be "device-related", as outlined below.

6.6.2 Stopping rules for SAEs that are device-related
Definition of Terms:
□ Screw failure – screw and/or centering staple have loosened from the vertebra AND require re- operation
☐ Tether failure – the tether has broken or lost tension. Diagnosed at any time point after 3 months by increased angulation at a disc space on standing PA or increase in disc wedging on side bending x-ray to the side away from the implant. Also, it is only an SAE if noted before maturity AND overall Cobb worsens compared to the first erect measurement
☐ Implant re-operation - any problem with the implant that requires re-operation including re-operation for overcorrection with any of the following: a removal of all or part of the implant, loosening of the tension on the implant, or spinal fusion.

Stopping Points
☐ Screw failure stopping point: 3 of first 5 cases, 5 of first 10, or 25% of patients beyond 20
cases
☐ Tether failure stopping point: 3 of first 5 cases, 5 of first 10, or 25% of patients beyond 20
cases
☐ Implant failure re-operation stopping point: occurs in 4 of first 5 cases or greater than 50% of
cases beyond 10 cases

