9.3.2 Risk Assessment

This section outlines risks associated with the study procedures.

9.3.2.1 Surgical Procedure: Anterior-approach thoracoscopic vertebral body tethering (greater than minimal risk)

1. Investigational devise risks:

Implant failure (tether breakage, lost tension, screw pullout, screw fracture) overcorrection of curve, failure of correction, progression of curve and need for conversion to spinal fusion. Reoperation for any of the above listed reasons.

2. Anesthesia Risks:

Anesthesia effects alone or with the effects of surgery can be life threatening. Injury to the eyes, lips, teeth, nerves and/or spinal cord, increased or decreased blood pressure, irregular heartbeat, abnormal reaction to anesthesia agents. Some other known risk, side effects and potential complications include nausea and vomiting after surgery, excessive bleeding requiring blood transfusions. There are certain (very rare) risks of anesthesia including stroke, blindness, and long-term learning disability, which are unpredictable, not well understood and still being studied by doctors.

3. Surgery Risks:

Infection, bleeding, allergic reaction, significant scarring, need for additional surgery, and even death or disability. Some other known risks, side effects and potential complications include neurological deficit, visceral, or vessel injury, blindness, need for transfusion of

blood products, back pain, pulmonary insufficiency, pain and unforeseen medical complications. Risks associated with radiation exposure from fluoroscopy and X-rays.

4. Spine surgery risks:

Implant malposition, implant failure (rod breakage, screw pullout, screw fracture), progression of curve above or below corrected spinal region, pseudoarthrosis (non-union), need for additional surgery, vertebral body damage, paralysis, and allergic reaction to implants. Reoperation for any of the above listed reasons.

It should be noted that the above risks are the same risks that are present for standard-of-care surgery for spinal surgery. All appropriate clinical care procedures and pathways followed for standard-of-care spine surgeries will take place for these subjects.

9.3.2.2 Other Potential Risks (No greater than minimal risk study procedures):

- Review of medical records: There is a risk of breach of confidentiality and privacy as a result of medical record review. This risk is minimized as detailed in Section 9.

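### The screw-failure stopping line counts loosening but not fracture, so an isolated screw fracture that is re-operated faces late limits above 50% instead of 25%

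*Combined protocol and SAP*

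**What the plan says.** Section 6.6.2 sets three device-related stopping lines.

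- **Screw failure** means that the "screw and/or centering staple have loosened from the vertebra AND require" re-operation. Its limit reads "Screw failure stopping point: 3 of first 5 cases, 5 of first 10, or 25% of patients beyond 20" cases.
- **Tether failure** means that "the tether has broken or lost tension". It counts as an SAE only if seen before maturity and with a Cobb angle worse than the first erect measurement. Its limits are the same: "Tether failure stopping point: 3 of first 5 cases, 5 of first 10, or 25% of patients beyond 20" cases.
- **Implant re-operation** means "any problem with the implant that requires re-operation including re-operation for overcorrection". Its limit reads "Implant failure re-operation stopping point: occurs in 4 of first 5 cases or greater than 50% of" cases beyond 10 cases.

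The general SAE rule (sections 6.6 and 6.6.1) halts at 5 of the first 5, 7 of the first 10, or more than 50% after 20 cases, for SAEs related to the study procedure.

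Elsewhere, section 9.3.2.1 lists the investigational device risks as "Implant failure (tether breakage, lost tension, screw pullout, screw fracture") together with overcorrection and other items. Section 5.2 names device breakage, alongside migration, as an example of a device-related event, and counts the vertebral screws among the device components.

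**The concern.** The protocol names two ways for a screw to fail, pullout and fracture, but the line called screw failure covers only loosening. Breakage counts for the cord and not for the screw, and no reason is given. Two screw failures with the same consequence, a re-operation, are therefore judged against different limits.

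This matters because the primary objective is safety, there is no comparison group, and section 6.4 declines any power calculation. The stopping rules are the plan's main quantitative safeguard for an investigational combination of screws, staples and cord. Section 6.6 says that device-related SAEs receive special consideration. After the early looks, an isolated screw fracture receives no limit below about half of the patients.

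**Working it through.** **1. Where a screw fracture counts**

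| Event | Screw line (25%) | Tether line (25%) | Re-operation line (>50%) | General SAE rule (>50%) |
|---|---|---|---|---|
| Fracture, no loosening, tension kept, re-operated | no | no | yes | if procedure-related |
| Fracture that also loosens, re-operated | yes | no | yes | if procedure-related |
| Fracture with lost tension and Cobb worsening before maturity | only if it also loosens and is re-operated | yes | if re-operated | if procedure-related |
| Fracture, no re-operation, no tether failure | no | no | no | only if otherwise an SAE |

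The last column follows from Appendix 1 and the SAE definition in section 8.4: surgical re-intervention is Clavien-Dindo grade III, and grade III and above are SAEs. The section on the relationship of events to the study intervention includes device implantation in that intervention.

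**2. Limits as patient counts**

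The total of 30 comes from the synopsis and section 3.3.2. I read the screw limit as at least 25% from case 21.

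- Case 21: 0.25 × 21 = 5.25, so 6 patients; 0.50 × 21 = 10.5, so 11 patients.
- Case 30: 0.25 × 30 = 7.5, so 8 patients; more than 0.50 × 30 = 15, so 16 patients.
- Early looks: 3 of 5 for the screw line against 4 of 5 (re-operation) and 5 of 5 (general). By case 10, 5 for the screw line against no re-operation limit and 7 (general).

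The 8-against-16 difference needs no assumed rate.

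**3. Chance of a halt by case 30**

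The plan states no error rates for these limits, so there is no figure to reproduce. I used an exact recursion with a look after each patient. Let f(n, x) be the probability of x events after n patients without a halt, and p the rate per patient:

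f(n, x) = (1 − p) · f(n−1, x) + p · f(n−1, x−1).

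At each n, the probability at any x that meets the rule is moved to the halt total. Screw rule: x ≥ 3 for n ≤ 5; x ≥ 5 for n = 6 to 10; x ≥ 0.25n for n > 20. Re-operation rule: x ≥ 4 for n ≤ 5; x > 0.5n for n > 10. General rule: x = 5 at n = 5; x ≥ 7 for n ≤ 10; x > 0.5n for n > 20.

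The documents give no rates. Assumed: loosening with re-operation 15%; isolated fracture with re-operation as shown; no patient with both; events independent and known at once. The last two columns use the total rate and count these screw re-operations alone, so other re-operations or SAEs would raise them.

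| Fracture rate | Total p | Screw rule as written (p = 15%) | Screw rule, both modes | Re-operation rule | General SAE rule |
|---|---|---|---|---|---|
| 1% | 16% | 17.1% | 21.1% | 0.7% | <0.1% |
| 2% | 17% | 17.1% | 25.5% | 0.9% | <0.1% |
| 5% | 20% | 17.1% | 40.1% | 1.9% | 0.2% |
| 10% | 25% | 17.1% | 64.6% | 5.3% | 1.1% |
| 15% | 30% | 17.1% | 82.9% | 12.0% | 4.1% |

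With loosening at 10% and fracture at 5%, the screw rule moves from 3.7% to 17.1%.

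**The case against.** **No strict contradiction.** Section 9.3.2.1 is a risk list headed implant failure and does not define screw failure. Section 6.6.2 has a line named for implant failure re-operation that takes any implant problem needing re-operation. Overcorrection is handled the same way: a listed risk, counted under that line. One can read a deliberate two-tier design, with tighter limits for loosening and tether failure and a catch-all for the rest. This stands as a reading. The text does not state it, and it does not explain why breakage is in the tighter tier for the cord but not for the screw.

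**Fracture is not left uncounted.** A reader might infer that a fracture never counts toward a 25% limit, or that it falls under the re-operation line alone. The documents do not support either inference: the second and third rows of the first table reach a 25% limit, and the general SAE rule can also apply. Neither the re-operation line nor the general rule closes the gap for an isolated fracture, because both late limits exceed 50%.

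**Other oversight exists.** The synopsis calls for a separate meeting whenever an SAE occurs, and for meetings before the 1st, 5th and 9th patients and so on. Relatedness is decided case by case, and unanticipated device effects are reported within 10 working days. That stands: the gap is in the numeric trigger, not in all review.

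**The size depends on assumptions.** A reader might take 17.1% against 82.9% as the effect. That pair needs a 15% fracture rate, for which the documents give no basis; at 1% to 2% the change is 4 to 8 percentage points. Events are also not known at once. Follow-up runs 5 years, while up to 15 patients a year would fill 30 places in 30 / 15 = 2 years, sooner with retrospective patients included. Under section 6.5 a met rule halts enrolment, so a fracture found after enrolment closes changes nothing under either limit.

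**Conclusion.** The point holds for the isolated screw fracture that needs re-operation. It lies outside the screw-failure definition although the protocol treats screw fracture as implant failure and breakage as device-related, and 16 rather than 8 of 30 patients are needed before a late limit is met. That asymmetry rests on the text alone, given a total of 30.

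The effect on the chance of a halt is uncertain. With 15% loosening, no overlap and immediate knowledge of events, it ranges from 17.1% against 21.1% when fracture is 1% to 17.1% against 82.9% when it is 15%. If fracture is rare or mostly late, little changes. It is worth correcting because it concerns a safety trigger and the change is confined to one definition.

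**What to change.** Reconcile the screw-failure definition in section 6.6.2 with sections 9.3.2.1 and 5.2, so that the screw stopping line covers the screw failure modes the protocol itself names: fracture as well as loosening or pullout. Keep the re-operation condition and all numeric limits as they are. Merely stating that fracture is left to the re-operation line would make the text explicit but would leave the asymmetry in place.

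The cost is a few words in one definition and a higher chance of an enrolment pause. That increase is small if fracture is rare (about 4 percentage points at an assumed 1%) and large only if fracture is common.
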